#### 4.4 Effectiveness analysis

The primary endpoint of this study is the success rate of breast-conserving surgery in patients with breast cancer. The success of breast-conserving surgery was determined by a negative tumor margin at least 2-3mm from normal tissue. Secondary endpoints included surgical specimen quality, functional outcome, and quality of life (postoperative pain score, postoperative cosmetic score).

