## Scenario summary

research topic	Application of Single-Port Robot-Assisted Breast-Conserving Surgery via Axillary Approach for Breast Cancer.
Main purpose of the study	
1. To evaluate the efficacy of single-port robots in breast cancer breast conserving surgery. Including differences in operative time and intraoperative number of lymph nodes detected.
 
2. To evaluate surgical safety: the incidence of surgical transfer and the incidence of postoperative complications.

Secondary purpose of the study	Pain and cosmetic scores of patients after breast conserving surgery under a single port robotic approach.
research design	
 Randomized controlled trial
 
 non-randomized controlled study
 
 Single-arm study
 
 Other
 
 Single-center study    multicenter study
 
Whether blind:  yes  no

subject investigated	Patients undergoing breast-conserving surgery for breast cancer.
intervention study	Single-port Robot-assisted breast-conserving surgery for breast cancer.
endpoint criteria	Success rate of breast conservation surgery under single-port robotic approach
sample capacity	Total number of cases: 100; 20 in the test group; 80 in the control group

statistical analysis	Double data entry was carried out using Excel 2010, and data analysis was performed with SPSS 25.0. The normality of continuous variables and homogeneity of variance were examined by Kolmogorov-Smirnov test and analysis of variance test respectively. For continuous variables that conformed to normal distribution and had homogeneity of variance, the independent-samples t-test was adopted. For continuous variables that did not conform to normal distribution, the Mann Whitney U test was used. For categorical variables and count data, Fisher's exact test and Pearson chi square test were employed.
Study cycle	November 2024-December 2025

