### 3.3.2 Exclusion criteria

- 1) Inflammatory breast cancer.
- 2) The tumor is extensive and it's difficult to achieve negative margins or an ideal breast - conserving appearance.
- 3) Diffusely distributed malignant - characteristic calcifications.
- 4) The margin is positive after local extensive tumor resection, and a negative margin in pathological examination still can't be ensured after re - resection.
- 5) The patient refuses.

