### 3.3.3 Exit criteria

- 1) Those who cannot complete the single-port robot breast conserving surgery and need to be converted into traditional breast conserving surgery or endoscopic breast preservation surgery.
- 2) The patient voluntarily requests to withdraw from the investigator.
- 3) The patient is associated with other non-tumor conditions so that they cannot continue to accept the study program;
- 4) After inclusion in the study, the investigator cannot be completed due to other reasons.

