### 3.8 Endpoint evaluation index

To verify the safety and efficacy of the single-port robot (SPr) in breast conserving surgery, the primary endpoint of this study was the success rate of breast conserving surgery. Successful breast-conserving surgery was determined by a negative tumor margin at least 2-3mm from normal tissue, and secondary endpoints included postoperative pain score and cosmetic score.

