#### 3.8.1 Primary endpoint indicators

Success rate of breast conserving surgery under single port robotic transaxillary approach.

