#### 4.3 Preliminary analysis

Two-person data entry was performed using Excel 2010 and SPSS 25.0 data analysis. Baseline numerical data will be described as mean, standard deviation or median and interquartile range, and baseline categorical data will be shown as percentage. Normality and homogeneity of variance of continuous variables were tested by Kolmogorov-Smirnov test and ANA variance, respectively. Independent sample t-test for continuous variables meeting normal distribution and homogeneity of variance, Mann Whitney U test for continuous variables not meeting normal distribution, and Fishers exact test and Pearson chi square test for categorical variables and count data. Primary endpoint analysis: The success rate of breast conservation surgery under single hole robot will be compared by Chi-square test (Chi-square test) with exact test if necessary. Use multiple interpolation methods to deal with missing data. Postoperative cosmetic score and postoperative pain score were calculated and analyzed according to the standard scale.

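### Failed robotic operations drop out of the primary success rate instead of counting against it, and a breast lost after a clear margin still scores as a success

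*SAP*

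**What the plan says.** Section 3.8.1 names the primary endpoint: "Success rate of breast conserving surgery under single port robotic transaxillary approach". The Scenario summary names it in similar terms. The scoring rule appears twice. Section 4.4 has: "The success of breast-conserving surgery was determined by a negative tumor margin at least 2-3mm from normal tissue". Section 3.8 says the same: "Successful breast-conserving surgery was determined by a negative tumor margin at least 2-3mm from normal tissue". Neither statement asks whether the breast was kept or whether the robotic operation was carried through.

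Other sections decide who is left to be scored:

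- Section 3.3.3, exit criterion 1, takes out patients whose robotic operation is not completed and who "need to be converted into traditional breast conserving surgery or endoscopic breast preservation surgery".
- Section 3.3.2, exclusion criterion 4, reads: "The margin is positive after local extensive tumor resection, and a negative margin in pathological examination still can't be ensured after re - resection".
- Section 4.2 is headed as the analysis population but defines no analysis set.
- Section 4.3 says the success rate "will be compared by Chi-square test (Chi-square test) with exact test if necessary". It also says missing data will be imputed, without saying whether patients who exit are treated as missing.
- The Scenario summary lists conversion under safety: "the incidence of surgical transfer and the incidence of postoperative complications".

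**The concern.** The endpoint's name promises three things: the breast is conserved, the robotic axillary route is the one used, and the result is oncologically adequate. The rule measures only the third. A new approach can fail in the other two ways as well, since the operation may not be completed robotically or the breast may be lost.

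A conversion should lower a rate described as success under the robotic approach. Under exit criterion 1 it removes the patient instead. Exclusion criterion 4 acts in the same way on the margin itself, because whether re-resection clears the margin is known only after surgery. A later mastectomy, for example after the necrosis or infection that section 5.1.1 lists, does not change the margin recorded at the first operation, so the score stays a success.

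Section 2 gives safety and feasibility as the purpose. A headline rate that never counts a conversion as a failure says little about feasibility.

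**Working it through.** **Inputs.** There are 20 robotic patients (Scenario summary and 4.1 agree). The plan gives no conversion rate, mastectomy rate or expected success rate, so there is no stated figure to reproduce and the counts below are assumptions. Let

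- c = robotic operations converted, all with clear margins;
- m = robotic operations completed, but with a margin that re-resection cannot clear.

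**Three ways to score the robotic group**

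- Plan as written, with exits and exclusions removed: (20 − c − m)/(20 − c − m).
- All 20 kept, margin-only rule: (20 − m)/20.
- Endpoint as named, over all robotic starts: (20 − c − m)/20.

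Exact (Clopper-Pearson) 95% intervals are in brackets.

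| c | m | Plan as written | All kept, margin only | Named endpoint, all starts |
|---|---|---|---|---|
| 1 | 0 | 19/19 = 100% (82.4 to 100) | 20/20 = 100% (83.2 to 100) | 19/20 = 95% (75.1 to 99.9) |
| 2 | 0 | 18/18 = 100% (81.5 to 100) | 20/20 = 100% (83.2 to 100) | 18/20 = 90% (68.3 to 98.8) |
| 3 | 0 | 17/17 = 100% (80.5 to 100) | 20/20 = 100% (83.2 to 100) | 17/20 = 85% (62.1 to 96.8) |
| 3 | 2 | 15/15 = 100% (78.2 to 100) | 18/20 = 90% (68.3 to 98.8) | 15/20 = 75% (50.9 to 91.3) |

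With all remaining margins clear, the plan's rate is 100% whatever c is, while the named endpoint is 1 − c/20. Each conversion is therefore worth 1/20 = 5 points. In the last row, if exit criterion 1 is applied but exclusion criterion 4 is not, the rate is 15/17 = 88.2% (63.6 to 98.5).

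**Later loss of the breast.** If d robotic patients with clear margins lose the breast by 90 days, the margin-only rule still gives 20/20, against (20 − d)/20 when a conserved breast is required. That is again 5 points each. In the control group one such patient is 1/80 = 1.25 points or 1/60 = 1.7 points, depending on which control size applies (Scenario summary 80, section 4.1 60).

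**Symmetry.** Exit criterion 1 can remove patients only from the robotic group. Exclusion criterion 4 can remove them from either.

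**The case against.** A reader might infer that a converted patient, or one whose robotic operation ended in mastectomy, is scored as a robotic success. The documents do not support that.

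- Exit criterion 1 withdraws patients converted to traditional or endoscopic conservation, so they are removed and not counted as successes.
- Exit criterion 4, although poorly worded, may cover an operation abandoned for mastectomy. The success rule also takes breast-conserving surgery as its subject, so an intraoperative mastectomy is at most unaddressed.
- A probability for how often such events occur cannot be drawn from the plan, which gives no rate. Pooling conversions with breast losses would also mix unlike events.

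Two further points are fair. Conversion is already a named safety measure, so the information is not necessarily lost. Complications are already followed at 28 and 90 days (3.1), and adding later breast loss to a pathology-based endpoint is partly a design choice.

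These points narrow the concern but do not remove it. Reporting conversion under safety leaves the headline rate unchanged. Whether converted patients are removed or kept, the written rule never counts a conversion with a clear margin as a failure. It might be said that exclusion criterion 4 refers to surgery before enrolment, but inclusion criterion 2 appears to rule out earlier chest surgery, so the study operation is the more natural reading. Later breast loss after a clear margin is reached by the literal rule: sections 3.8, 4.3 and 4.4 contain nothing that would rescore it.

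**Conclusion.** The concern holds in this form: the name of the primary endpoint and its scoring rule do not match, and the exit and exclusion criteria, with no analysis set defined, take robotic failures out of both numerator and denominator. The overstatement is 5 points per converted robotic patient. With 1, 2 or 3 conversions the plan gives 100%, against 95%, 90% or 85% of all robotic starts. This rests on assumed counts and on all remaining margins being clear. The written rule can still record a failure on the margin itself in a patient who stays in. A breast lost later after a clear margin counts as a success; the documents give no indication of how often that would happen.

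**What to change.** 1. In 3.8 and 4.4, define success for the between-group comparison, in both groups, as breast conserved at the existing 90-day time point **and** negative margin. Any mastectomy by then is a failure.
2. In 4.2, define the primary analysis set as all patients who start the planned operation, kept in the group of that operation. State that exit criterion 1 and exclusion criterion 4 may end study treatment but do not remove the patient from the primary analysis.
3. For the robotic-group rate in 3.8.1, report the proportion of all robotic starts completed without conversion, with the breast conserved and a clear margin. Completion belongs only in this rate, because controls cannot convert.

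The first change alone is not enough: if exited patients stay out of the denominator, the rate is still inflated. With all three, a robotic case converted with a clear margin and a conserved breast counts as a success in the comparison and as a failure in the robotic-group rate, which answers both questions openly.

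The cost is mainly SAP wording. The conversion measure and the 90-day time point exist, and the cosmetic score is already collected at the 3-month visit (3.6). Breast status has to be added as an item, converted patients have to be followed to 90 days, and the stated success rate may be somewhat lower.

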#### 4.5 Safety analysis

SPr-breast conserving surgery, as a relatively new surgical method, is still under continuous exploration. Surgical risks and complications related to intraoperative and postoperative hemorrhage, flap or nipple areola complex necrosis, subcutaneous emphysema, infection, capsule and capsular spasm, and postoperative shoulder pain and discomfort may occur during the surgical procedure and perioperative period. The difference between SPr-surgery and open-surgery lies in the different surgical approach platform, and the surgical operation procedure and principles are basically the same. In the early stage, our department has carried out more than 200 cases of Da

Vinci multi-arm robotic (Xi or Si surgical system) surgery, accumulated the experience of robotic surgery, and verified the feasibility and safety, and laid a solid foundation for the smooth development of this study. In addition, our department has rich experience in handling various perisurgical complications of breast cancer surgery, and can properly handle the perioperative complications of breast cancer surgery. Adverse events were recorded in detail and discussed during the trial.

## 5. Safety evaluation and disposal

Including possible adverse events and their definitions, evaluation method of correlation between adverse events and the study, severity assessment of adverse events, handling of adverse events, follow-up and reporting of serious adverse events.

### 5.1 Adverse events

#### 5.1.1 Definition

(1) Intraoperative and postoperative bleeding and hematoma: the phenomenon of blood vessel rupture at the surgical site and blood outflow outside the blood vessels. After breast preservation surgery for breast cancer, bleeding may be caused by incomplete intraoperative hemostasis, or shedding of postoperative vascular ligation line, abnormal coagulation function, and increased local vascular pressure. The hematoma is a mass-like structure formed by blood accumulation in the local tissue of the operation. It is a consequence manifestation after bleeding. With the continuous accumulation of blood, the formation of hematoma area with a certain boundary, which produces pressure on the surrounding tissue.

(2) Breast flap necrosis: In breast cancer, the skin and subcutaneous tissue flap with blood supply is cut from the supply area (such as the skin tissue around the breast) to cover the surgical wound or reconstruction of partial breast structures. Breast flap necrosis refers to the situation of this part of the flap due to insufficient blood supply, infection and other factors, resulting in tissue cell death. The flap color will gradually become black and harden, lose elasticity and luster, and eventually may appear dry necrosis (such as leather-like changes) or wet necrosis (with exudation, suppuration, etc.).

(3) Necrosis of nipple areola complex: nipple areola complex includes nipple and

areola. The necrosis of nipple areola complex refers to the necrosis of nipple and (or) areola tissue due to the destruction of blood transport (such as cutting off the main blood vessels), local tension, infection and other factors. The nipple areola will appear color change (such as from pink to dark black), sensory loss, the later stage may fall off the tissue and other phenomena.

(4) Subcutaneous emphysema: a pathological phenomenon in which gas enters and accumulates in the subcutaneous tissue space after breast-conserving surgery. Under normal circumstances, there is no gas in the subcutaneous tissue. When the gas (mainly air) enters the subskin through the surgical wound or the damaged area of the surrounding tissue, and forms a certain area of emphysema, subcutaneous emphysema appears.

(5) Infection: the pathological process of bacteria, fungi, viruses and other invade the incision site, and grow and reproduce in it, causing local inflammatory reaction and (or) systemic reaction. After breast conserving surgery in breast cancer, the skin and tissue integrity. When the sterile environment of the operating room is not up to standard, the surgical instruments and dressings are not thoroughly disinfected, the concept of aseptic is not strong during the operation, the patients immunity is low (such as diabetes, malnutrition, etc.), or the postoperative incision care is improper (such as not changing the dressing in time, wound exposure to contamination, etc.).

(6) Envelar spasm: the process of contraction, thickening and hardening of the fiber capsule around the breast implant. This coating was supposed to be soft and elastic to accommodate the implant and maintain the natural shape and softness of the breast. But during the capsular contracture, it is gradually tightened, squeezing the implant.

(7) Postoperative shoulder pain: shoulder-centered pain sensation in the patient after breast conserving surgery. The pain can be unilateral (usually the shoulder on the affected side) or may involve both shoulders, but is more pronounced on the affected side.

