## 1. Research Background

Breast cancer is the second most prevalent female malignancy in China[1]. At present, the most important treatment for breast cancer is still surgical treatment[2-5]. Surgical treatment is inevitable in many cases, and with traditional surgery, it does leave a permanent scar on the chest[6]. Patients with high requirements for breast and breast aesthetic requirements are troubled by this. Studies show that young women of Asian descent (<50 years old) have more dense breasts than white women in the US[7]. So, it is more likely to the scars happen, and the scar repair after breast surgery is also more slow[8,9]. Therefore, minimally invasive breast surgery is necessary for Chinese women. Clinically, breast surgeons carry out different minimally invasive surgical methods and use different surgical approaches (such as axillary approaches) to achieve scar-free and attractive breast cancer surgery.[10,11]

The minimally invasive surgical approach enables better wound healing and less postoperative pain with the same tumor removal effect as open surgery[12]. Robotics is one of the widely used minimally invasive surgery in breast surgery, compared with open surgery, this minimally invasive technique reduces the occurrence of postoperative complications, enhances the protection of limb function, and meets the needs of patients for beauty. The study data showed that the postoperative complication rate of traditional open surgery was 7%, while the complication rate after robotic surgery was only 3.9%[13-15]. At the same time, in addition to the advantages of minimally invasive technology, robotics has its unique characteristics[16-18]. The application of robot technology makes breast surgery realize remote, digital and intelligent. Compared with the endoscopic surgery system, the robot system has a three-dimensional high-definition visual field magnified tens of times, so that the surgeon can have a clearer surgical vision, improve the surgical resolution, and increase the control of the operation. Moreover, the robots rotating wrist surgical instrument arm can rotate for 540°, enabling intuitive movement for a

more flexible and delicate operation[19]. For breast surgery with a narrow surgical area, the application of robotics is particularly important.

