## 3. Research Design

### 3.1 Overall Study Design

-Enrollment: Subjects who meet the inclusion criteria enter the study process, including SPr-breast conserving surgery or Traditional-breast conserving surgery. The choice of the two surgical methods is based on the patients economic situation and the availability of equipment.

-Preoperative hospitalization: Collect patient disease information (including mammography, breast B ultrasound, breast enhanced MRI, etc.).

-The day of operation: Record the operation time, intraoperative bleeding volume, intraoperative complications, intraoperative adverse events, etc.

-Postoperative hospitalization: Record postoperative complications (postoperative bleeding, flap or nipple areola complex necrosis, subcutaneous emphysema, infection, capsular spasm, postoperative shoulder pain and discomfort, etc.), postoperative pain score, and postoperative pathological biopsy.

-Postoperative hospital stay: Calculated based on the number of days from surgery to discharge.

[figure not shown]
-28 days after surgery: To understand the complication rate and mortality rate within 28 days after surgery.

-90 days after surgery: To understand the complication rate and mortality rate within 90 days after surgery.

-Disease-free survival at 3 years after surgery (recurrence was defined as surgical area and distant metastasis by the time from surgery to last follow-up or date of recurrence and metastasis).

-3 year overall survival (from time from surgery to last follow-up or death).

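### Bleeding and shoulder pain count as postoperative complications with no threshold or grade, so minor events can inflate the complication rate and dilute or bias the comparison

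*SAP*

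**What the plan says.** The Scenario summary makes safety the second main purpose: "To evaluate surgical safety: the incidence of surgical transfer and the incidence of postoperative complications". Section 3.1 then asks for complication rates at 28 and 90 days and gives the list to record: "Record postoperative complications (postoperative bleeding, flap or nipple areola complex necrosis, subcutaneous emphysema, infection, capsular spasm, postoperative shoulder pain and discomfort, etc".

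The only definitions of these events are in section 5.1.1:

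- Item (1), bleeding and haematoma: "Intraoperative and postoperative bleeding and hematoma: the phenomenon of blood vessel rupture at the surgical site and blood outflow outside the blood vessels". One definition serves both intraoperative and postoperative bleeding. It gives no volume, intervention, grade or time criterion.
- Item (7): "Postoperative shoulder pain: shoulder-centered pain sensation in the patient after breast conserving surgery". It gives no score, duration or window.
- Item (6), the capsular event: "the process of contraction, thickening and hardening of the fiber capsule around the breast implant". Section 3.5 describes no implant in either group.

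Section 5.1.2 grades events as mild, moderate or severe according to their effect on daily life. It does not say which grades enter the complication rate. Section 4.5 says only that adverse events are recorded and discussed. The Scenario summary describes a non-randomised, unblinded study.

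**The concern.** A complication rate is comparable between groups only if two recorders looking at the same patient would make the same call. Here that call has no boundary. A small ooze under the dressing and a haematoma needing evacuation both fit item (1). A transient ache and disabling pain both fit item (7). A patient with either counts as having had a complication.

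Two consequences follow.

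- **Dilution.** If trivial events are about equally common in both groups, they add the same background to each and shrink any real difference.
- **Bias.** Recorders know which operation was done, and one group is operated on through the axilla. How readily minor bleeding or shoulder discomfort is noted may therefore differ by group, and the difference can move in either direction.

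The complication part of a main purpose is at stake. So is comparability with the background rates that the plan itself cites in section 1.

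**Working it through.** **No figure to reproduce.** The SAP gives no expected complication incidence under its definitions, and no alpha, power or effect size behind its group sizes. What follows shows direction and sensitivity only.

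**Inputs**

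- Background complication rates (section 1): 7% open, 3.9% robotic. They are used here as rates c of non-trivial complications. The plan does not use them as planning values.
- Group sizes: 20 robot patients. The control group is 80 in the Scenario summary and 60 in section 4.1, so both are run.
- Trivial-event rate m: not in the SAP. Assumed, and shown over a range.
- Further assumptions: all event types pooled into one any-event rate, trivial events independent of real complications, two-sided alpha of 0.05.

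**Step 1: dilution with the same m in both groups**

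Any-event rate = 1 − (1 − m)(1 − c), so the group difference is (1 − m) × (7.0 − 3.9) = (1 − m) × 3.1 points.

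| Assumed m | Robot | Open | Difference (points) |
|---|---|---|---|
| 0% | 3.9% | 7.0% | 3.1 |
| 25% | 1 − 0.75 × 0.961 = 27.9% | 1 − 0.75 × 0.93 = 30.3% | 2.3 |
| 50% | 1 − 0.50 × 0.961 = 52.0% | 1 − 0.50 × 0.93 = 53.5% | 1.6 |
| 90% | 1 − 0.10 × 0.961 = 90.4% | 1 − 0.10 × 0.93 = 90.7% | 0.3 |

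**Step 2: bias with a different m in each group**

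If m were 50% in the robot group and 25% in the open group, the rates would be 52.0% and 30.3%. The robot would look about 21.7 points worse although its underlying rate is 3.1 points lower. With the two values swapped, the rates are 27.9% and 53.5%, about 25.6 points in the robot's favour. Differential recording therefore matters more than dilution.

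**Step 3: does a large safety signal survive dilution?**

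Assume true rates of 30% (robot) and 5% (open). Power of the two-sided Fisher test, by exact enumeration:

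| Assumed m | 20 vs 60 | 20 vs 80 |
|---|---|---|
| 0% | 78% | 83% |
| 50% | 14% | 16% |
| 90% | 1% | 1% |

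**Step 4: what a threshold cannot do**

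With m = 0 and true rates of 3.9% and 7%, Fisher power is about 0.4% to 0.5% with 20 robot patients and either control size. Power of 80% would need 588 robot patients at 1:3 or 556 at 1:4. A counting threshold makes the rate interpretable and protects a large signal. It does not make a 3.1-point difference detectable.

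**The case against.** A reader might infer something stronger: that every operation meets item (1), so the incidence approaches 100% in both groups and the safety objective cannot be answered. The SAP does not support this, for five reasons.

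- The objective concerns postoperative complications. Section 3.1 lists bleeding there as postoperative and records intraoperative blood loss as a volume on the day of operation. The schedule in 3.6 also gives intraoperative bleeding its own row. Routine operative blood loss therefore need not enter the rate.
- Item (1) goes on to name abnormal causes, such as incomplete haemostasis, a slipped ligature or a clotting disorder. It is not plainly aimed at the ordinary bleeding of an incision.
- No section pools all event types into one any-event rate.
- The implant-only event has an expected rate of 0% where no implant is placed. It cannot push the incidence up.
- Conversion, the other half of main purpose 2, is untouched, and rates by event type remain reportable.

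There are further fair points. The reference titles behind the 7% and 3.9% concern axillary dissection and nipple-sparing mastectomy, so these figures are a loose guide to breast-conserving surgery. Counting rules may also sit in the protocol or in the CRF filling instructions mentioned in 6.2, neither of which is shown.

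These points remove the near-100% claim but leave the narrower one standing. Postoperative bleeding takes its meaning from the same item (1), whose list of possible causes sets no minimum. Section 4.5 names intraoperative as well as postoperative haemorrhage among the complications. Item (7) is wholly postoperative, so the first two reasons do not touch it. The weakness also lies in definitions that the SAP does state, and is more than detail left to another document.

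**Conclusion.** The point holds in limited form. The bleeding and shoulder-pain definitions set no counting threshold, and the 5.1.2 grades are tied to no rate. The complication component of main purpose 2 is therefore open to inflation by trivial events, in a setting where recorders know the operation and patients were not randomised.

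The size cannot be fixed from the SAP. On the pooled, equal-rate assumption, a 3.1-point difference becomes 2.3, 1.6 or 0.3 points at trivial-event rates of 25%, 50% or 90%. Unequal recording could shift it by more, in either direction. Every one of these figures depends on an assumed trivial-event rate and on pooling that the SAP neither specifies nor excludes.

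Conversion incidence is unaffected. The capsular item is inapplicable but changes no result.

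**What to change.** 1. In 5.1.1, state that postoperative bleeding or haematoma enters the complication rate only when it leads to an additional intervention or a prolonged stay, and define prolonged in advance. Keep ordinary blood loss under the bleeding volume that is already recorded.
2. Keep shoulder pain as a listed complication, but count it in the main rate only from a pre-stated 5.1.2 grade, for example moderate or worse. Moving it out of the complications altogether is not advised. The plan lists it deliberately, the axillary approach may provoke it, and its removal could favour the robot group. The general pain score is not described as shoulder-specific and may not replace it.
3. Report the 28- and 90-day rates by event type and grade, and list all-grade events beside them.
4. As a tidy-up with no effect on the rate, remove the capsular item from 3.1, 4.5, 5.1.1 and 8.1.

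The cost is wording in the SAP and on the CRF. No extra patients, visits or procedures are needed, and the grades are already defined in 5.1.2. The small downside is that minor events leave the main rate. They stay visible in the all-grade listing.
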